4.6.1 Exposure to Study Medication

Exposure data will be listed for both study drugs. The listing will show the randomized treatment as well as the treatment actually received.

A summary of exposure to alteplase/alteplase placebo will be produced for the safety population. The total dose administered and duration of infusion will be summarized by active or placebo Alteplase, as actually received. For Aspirin, dose received will always be “325 mg”, and therefore will not be summarized.

Compliance with study medications will be summarized for the safety population. For Alteplase, counts of infusion altered or stopped prematurely will be tabulated along with the reason. For aspirin, the number of patients who did not take study aspirin and a summary of reasons will be presented.

4.6.2 Adverse Events

AE safety endpoints in this study are:

- Number and percentage of patients experiencing serious and non-serious AEs after receiving study drug
- Number and percentage of patients experiencing serious and non-serious AEs of special interest

AEs will be coded (using the latest MedDRA version at the time of reporting) and tabulated by system organ class (SOC); individual events within each SOC coded as preferred terms will be presented in descending frequency using the safety population. Treatment groups will be summarized according to the actual treatment received.

AEs will also be tabulated by intensity (severity) and relationship to study drug, as indicated by the investigator. Intensity of AEs will be graded according to the WHO Toxicity Grading Scale for Determining the Severity of Adverse Events (see Appendix 14 of the protocol). Incidence and severity of AEs will be described for all treated patients by treatment group and by the MedDRA classification.

A summary of incidence rates of all deaths and stroke-related or neurological deaths will be presented. Cumulative incidence of all deaths and stroke-related or neurological deaths will be presented by means of Kaplan-Meier plots if there are sufficient events (at least 5 in each group).

Timing of the AEs relative to Day 30 and Day 90 will be determined, using imputation for partial AE start and stop dates if necessary, as described in [Appendix D](#). AEs occurring after receipt of any study medication and before Day 90 will be summarized. AEs leading to IV study drug modification will be listed. SAEs, ICH, AEs of special interest and AEs leading to study treatment discontinuation will be summarized through Day 90. In addition, non-serious AEs within 30 days will be summarized.

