Appendix F Data Handling Rules

Appendix G Programming Codes for Statistical Analysis

1. BACKGROUND

Stroke is the fourth leading cause of death and a leading cause of disability in the United States (U.S.). More than half of all ischemic stroke patients have mild strokes at initial presentation in population-based studies (3; 10). Alteplase is the only approved therapeutic agent for the treatment of AIS (acute ischemic stroke) and is widely accepted as the standard of care for eligible patients (4; 6). The currently approved Activase® (alteplase) U.S. Package Insert (USPI) contains wording that recommends against use of alteplase in patients with “minor neurological deficit or with rapidly improving stroke symptoms” due to the fact this patient population has not been evaluated. Furthermore, the current American Heart Association/American Stroke Association Council Guidelines include “minor and rapidly improving stroke symptoms (clearing spontaneously)” as a relative exclusion criterion for alteplase (6). This is largely due to the aforementioned label wording not recommending treatment of patients with minor neurological deficit or with rapidly improving stroke symptoms (RISS), the lack of a consistent and consensus definition of who constitutes this patient population, and the absence of definitive evidence of alteplase efficacy in this setting (TREAT Task Force 2013). Therefore, this trial is designed to evaluate the efficacy and safety of alteplase in confirmed AIS patients with minor neurological deficit or with RISS, which will be referred to collectively as “mild stroke”.

For further background information see Section 1 of the protocol.

The original plan was for approximately 948 patients with mild stroke to be enrolled and randomized in a 1:1 ratio to two treatment groups. However the study enrollment was prematurely terminated due to recruitment below target in December 2016 (at approximately 1/3 of original planned enrollment of 948) and the analysis will be performed using available data from patients randomized prior to study termination.

This Statistical Analysis Plan (SAP) describes the statistical methods to be used for the clinical study report of study ML29093. This version of the SAP has been developed using version 3 of the study protocol dated 08 Jan 2015. The SAP will be finalized by [REDACTED] and approved by Genentech, Inc. before database lock and unblinding.

Statistical Analysis Plan: Alteplase—Genentech USMA

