2.2.4 Safety Outcome Measures

The safety outcome measures for this study are as follows:

- Symptomatic Intracranial Hemorrhage (sICH) within 36 hours of receiving IV study drug (primary safety assessment)

sICH is defined as any neurological decline attributed to new ICH seen on imaging by the investigator (based on AE reporting). New ICH seen on imaging will be later confirmed on independent reading by blinded central study radiologists
- Any ICH (based on central neuroimaging reading) within 36 hours of receiving IV study drug
- Mortality within 90 days

Statistical Analysis Plan: Alteplase—Genentech USMA
7/ML29093 5/17/2017

- Stroke-related and neurological deaths within 90 days
- Incidence, severity, and spectrum of all adverse events (AEs) and serious AEs (SAEs).

The exploratory safety measure for this study is:

- Stroke recurrence (based on AE monitoring) within 90 days

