2.3 DETERMINATION OF SAMPLE SIZE

The sample size was originally determined as follows.

A sample size of 856 is required in order to achieve 80% power in the primary analysis to detect effect size of 9% absolute difference in the proportion of patients with favorable outcomes [mRS of 0 or 1 at Day 90] between the alteplase and control arms. The above power consideration assumes a control proportion of 65% and Type I error of 0.025 (one-sided), and uses a group sequential design with one interim analysis for futility (non-binding), based on O'Brien and Fleming boundary, conducted after 50% of the anticipated sample size have completed 90-day follow-up assessments. [REDACTED] was used in sample size calculation.

The intention-to-treat principle will be applied to the primary analysis and, therefore, to safeguard against dilution of the treatment effect associated with an approximate 5% non adherence rate (due to loss to follow-up, consent withdrawal, treatment crossovers and stroke mimics), the above sample size was inflated by a factor of 1.108 (5). Therefore, a total sample size of 948 was planned for this study.

The study enrollment was terminated early in December 2016, after 313 patients were randomized. The analysis will be carried out based on all available data from patients randomized prior to termination. With this sample size, power calculations show that the study will be substantially underpowered to conduct superiority tests (Table 1). Therefore, all efficacy analyses will include estimation of treatment effects with the associated two-sided 95% confidence intervals.

Table 1			
Estimated Power for the Final Sample Size (N=313)			
Assumed Effect Size	7%	8%	9%
Statistical Power ^a	25%	31%	38%
^a Based on the t-test for the observed proportions of mRS 0-1 at Day 90, using type I error of 0.025, one-sided. Assumptions are based on a blinded evaluation of non-adherences in the Jan 2017 Development Safety Update Report (DSUR) dataset: - Control response rate among confirmed strokes is 74%. - 10% of randomized subjects are stroke mimics and 80% of those stroke mimics will have favorable outcome. - 1% of subjects received concomitant tPA - 7.4% subjects without Day 90 outcome (290 effective sample size)			

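### Kaplan-Meier is planned as the cumulative incidence of stroke-related or neurological death, although it does not estimate that quantity when patients can die of other causes; the numerical effect is small

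*SAP*

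**What the plan says.** SAP section 2.2.4 lists two separate mortality outcomes among the safety measures: "Mortality within 90 days" and "Stroke-related and neurological deaths within 90 days". The second is a subset of the first, defined by cause.

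Section 4.6.2 plans two displays for them. One is a table: "A summary of incidence rates of all deaths and stroke-related or neurological deaths will be presented". The other is a plot: "Cumulative incidence of all deaths and stroke-related or neurological deaths will be presented by means of Kaplan-Meier plots". The plot depends on a count: "if there are sufficient events (at least 5 in each group").

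Section 4.6.6 adds mortality incidence by group and overall, and individual listings of deaths. The SAP does not say how a death from another cause enters the stroke-related or neurological curve, and it names no competing-risk estimator.

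**The concern.** One estimator is fixed for two outcomes of different kinds, and both results are called cumulative incidence. For all deaths there is no competing event, so one minus Kaplan-Meier estimates what the label says. For death from one group of causes, a patient who dies of something else can no longer have the event. Standard Kaplan-Meier knows only event or censored, so it treats that patient as if still at risk of stroke death later. The label and the method then disagree.

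At stake is how the figure is read. The outcome is a named safety outcome in a thrombolysis trial, and its curve is planned alongside the all-death curve. A reader would naturally take the first as a component of the second, and with Kaplan-Meier it need not be.

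**Working it through.** The SAP states no death rate, cause split or plotted value, so there is no figure to reproduce. The check is how far the two estimators can differ at Day 90.

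**Inputs from the SAP**
- Patients: "The study enrollment was terminated early in December 2016, after 313 patients were randomized" (2.3), "randomized in a 1:1 ratio to two treatment groups" (section 1). 313/2 ≈ 156 per arm. The safety population (treated patients) may be slightly smaller.
- Smallest number of counted deaths per arm: 5, the display rule in 4.6.2.
- Loss to follow-up, by proxy: "7.4% subjects without Day 90 outcome (290 effective sample size") in 2.3; 0.074 × 156 ≈ 12 per arm.

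**Assumed:** the numbers of counted deaths (a) and other deaths (b) per arm, and that other deaths are censored, as in standard Kaplan-Meier.

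**Formulas without loss to follow-up, N = 156**
- Aalen-Johansen at Day 90: a/N.
- One minus Kaplan-Meier, causes evenly mixed over time: about 1 − (1 − (a+b)/N)^(a/(a+b)). For 5 + 5: 1 − √(1 − 10/156) = 3.26%. Simulated averages over 2,000 sets of uniform death times agree with this to the digits shown.
- One minus Kaplan-Meier, all other deaths first (largest excess): a/(N − b). For 5 + 5: 5/151 = 3.31%.

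| Counted + other deaths | Aalen-Johansen | 1 − KM, average | Excess (points) | 1 − KM, other deaths first |
|---|---|---|---|---|
| 5 + 0 | 3.21% | 3.21% | 0 | 3.21% |
| 5 + 1 | 3.21% | 3.22% | 0.01 | 3.23% |
| 5 + 5 | 3.21% | 3.26% | 0.05 | 3.31% |
| 5 + 10 | 3.21% | 3.31% | 0.11 | 3.42% |
| 10 + 10 | 6.41% | 6.63% | 0.22 | 6.85% |
| 20 + 20 | 12.82% | 13.77% | 0.95 | 14.71% |

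The excesses are average 1 − KM less Aalen-Johansen, before rounding. If every counted death precedes every other death, the excess is zero.

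**Adding up.** Without ties, the Kaplan-Meier survival curves for the two causes multiply to the all-death survival curve. The two values of one minus Kaplan-Meier therefore exceed the all-death value by their product:
- 5 + 5: 0.0326² = 0.0011, or 0.11 points
- 10 + 10: 0.0663² = 0.0044, or 0.44 points
- 20 + 20: 0.1377² = 0.0190, or 1.90 points

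The Aalen-Johansen components add up exactly.

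**With loss to follow-up.** Adding 12 lost patients per arm to the 5 + 5 case gives 3.40% for one minus Kaplan-Meier and 3.34% for Aalen-Johansen, a gap of about 0.06 points. Ordinary censoring leaves the gap much as it was.

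**The case against.** The strongest reply is that nothing a reader would notice depends on this. One death in 156 is 0.64 percentage points, so an excess of 0.1 points is about one-sixth of a patient. The plot may never be drawn, because it needs at least 5 events in each group among 313 patients with mild stroke, and the synopsis in Appendix A excludes serious, advanced or terminal illness that would confound the 90-day outcome. No test, interval or decision is attached to it. The tabulated incidence and the death listings are separate.

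The larger scenarios also strain the SAP's own assumptions. Table 1 takes 74% of control patients with confirmed stroke to have a favorable outcome, which leaves 26% unfavorable, deaths included. The 20 + 20 case is 40/156 = 25.6% mortality, so nearly every unfavorable outcome would be a death. It is shown only to bound the effect.

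All of this stands, and it limits the importance of the point. It does not make Kaplan-Meier an estimate of the quantity named in 4.6.2.

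A reader might infer that the plotted stroke-death risk will be too high in both arms, or that the comparison between arms will be distorted. The SAP does not support either. The excess depends on deaths from other causes coming first, and the SAP gives no counts, causes or timing; even the censoring of other deaths is inferred from the name of the method. If one arm had 10 other deaths and the other 2, with 5 counted deaths in each, the shift would be 3.313% − 3.226% = 0.09 points, about one-seventh of a patient.

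**Conclusion.** The point holds as a mismatch between estimator and label in one descriptive safety plot. For stroke-related or neurological death, one minus Kaplan-Meier with other deaths censored is at or above the Aalen-Johansen cumulative incidence, and above it only where another death precedes a counted one in that arm.

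Near the display threshold, with up to 10 other deaths per arm, the excess averages at most about 0.1 percentage points and reaches about 0.2 in the least favorable ordering. These sizes rest on assumed death counts and 156 patients per arm. The all-death curve is correct as planned, and the incidence summaries are unaffected if they are crude proportions. This is a minor correction, worth making because it is nearly free; no conclusion of the trial is likely to depend on it.

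**What to change.** In section 4.6.2, keep Kaplan-Meier for all deaths. For stroke-related or neurological deaths, plot the Aalen-Johansen cumulative incidence function by arm, with deaths from other causes as the competing event and loss to follow-up as censoring. State that rule in the same sentence, since the SAP now gives none.

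The cost is one sentence and one option in the survival procedure. The data needed are death dates and the cause classification that the planned summaries already require. The stroke-related curve can then be read as a part of the all-death curve.

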4.6.2.2 Adverse Events of Special Interest

Non-serious AESIs are required to be reported by the investigator to the Sponsor immediately (i.e., no more than 24 hours after learning of the event; see Section 5.4.2 of protocol for reporting instructions).

Statistical Analysis Plan: Alteplase—Genentech USMA
26/ML29093 5/17/2017

AESIs for this study include the following:

- sICH events, if not already reported as an SAE (for a list of preferred terms for ICH see Appendix 13 of protocol)
- Stroke recurrence, if not already reported as an SAE.
Stroke recurrence is defined as a new ischemic stroke based on the AE reporting. Stroke events will be identified through a medical review of the AE preferred terms.
- Suspected Transmission of an Infectious Agent via a Medicinal Product (STIAMP) by the study drug, if not already reported as an SAE.

AESIs will be tabulated by SOC and preferred term within SOC by treatment group using the safety population.

4.6.3 Neuroimaging

Neuroimaging may consist of a non-contrast computed tomography (CT) or magnetic resonance imaging (MRI) of the brain. Non-contrast CT or MRI will be performed at baseline to ensure that the patient does not have evidence of acute intracranial hemorrhage (ICH) prior to study drug administration.

An additional non-contrast CT or MRI will be performed at 22 to 36 hours from the initiation (bolus) of study drug infusion. The purpose of this is to evaluate for ICH in the patient. Additional CT scans or MRIs should be performed based on the investigator's discretion, or if any clinical findings suggest ICH.

All CT and MRI scans will be evaluated by a central team of radiologists blinded to the clinical attributes of the case. Results from the evaluation of the CT or MRI scans by both local and central readings will be listed, as available.

4.6.3.1 Intracranial Hemorrhage

Intracranial hemorrhage events (ICH) are identified by neuroimaging and are recorded as AEs using one of the terms specified in protocol Appendix 13. The images obtained within the first 36 hours after treatment are further evaluated by central reading, which may or may not confirm ICH.

While ICH may be identified at any time during the study, the first 36 hours after treatment are the key time interval. If multiple scans indicate ICH within 36 hours, it is interpreted as a single ICH event. ICH events identified after the first 36 hours will contribute to the general AE summaries. Timing of ICH will be determined according to the rules specified in [Appendix D](#).

Incidence of ICH within 36 hours by AE reporting will be presented by treatment group. Determination of ICH within 36 hours from local and central readings of scans will also be presented, and agreement between the local and central readings will be tabulated.

Difference in percentage of subjects with ICH within 36 hours based on central and local scan reading will be reported by treatment group. A two-sided 95% CI around this difference will be constructed using the Miettinen-Nurminen score method (20).

Additionally, central reading classifications will be used to further describe subtypes of any ICH.

The central reading will classify ICH according to the following intracerebral subtypes:

- Hemorrhagic infarct type 1 or type 2
- Parenchymal hematoma type 1 or type 2
- Remote intraparenchymal hemorrhage type 1 or type 2

In addition, subarachnoid hemorrhage, subdural hemorrhage, or epidural hemorrhage will be noted. ICH subtypes will be tabulated by treatment group.

4.6.3.2 Symptomatic Intracranial Hemorrhage

The protocol specifies that ICH is considered symptomatic (sICH) if it is not seen on CT or MRI scan at baseline, and any neurologic decline is attributed to it by the local

investigator. Both serious sICH and non-serious sICH events are required to be reported by the investigator to the Sponsor immediately.

sICH within 36 hours is considered the primary safety outcome. sICH events are captured through AE reporting.

In addition to the primary definition of sICH, the following two definitions of sICH will be explored and reported in this study.

- sICH using Heidelberg classification: either (1) PH2 as reported by radiology core, or (2) an sICH as classified by PRISMS but also associated with 4-point total NIHSS score worsening or 2 point worsening on any single NIHSS item when comparing scores immediately pre and post scan.
- sICH using SITS-MOST definition (25): PH2 as listed by radiology core on CT scan between 22-36 hours, which is associated with deterioration of ≥ 4 points on the NIHSS from the lowest NIHSS value between baseline and 36 hours, but prior to repeat CT, or leading to death.

Percentage of subjects with sICH within 36 hours will be presented for each definition by treatment group. Difference between treatment group percentages will be reported along with a two-sided 95% CI constructed using the Miettinen-Nurminen score method (20).

ICH symptomatology will be tabulated for confirmed strokes and separately for stroke mimics.

4.6.4 Laboratory Data

Specimens for the laboratory tests will be analyzed by the site's local laboratory. Tests will be done at screening only and will include hematology (complete blood count without differential), serum glucose, coagulation values (INR, partial thromboplastin time), and pregnancy test.

Lab results will be converted to SI units and summarized as part of the baseline treatment group comparability described in Section 4.3; no further analysis is planned.

4.6.5 Vital Signs

Vital signs will be collected at screening, and will include measurements of pulse and systolic/diastolic blood pressure (while patient is in a supine position).

Vital signs will be summarized as part of the baseline treatment group comparability described in Section 4.3.

4.6.6 Mortality

Incidence of mortality will be calculated by treatment group and overall. Details of any deaths will be presented in the form of individual patient listings.

4.6.7 Previous and Concomitant Medications

Previous medications refer to those stopped prior to study day 1. Previous medications will be summarized by medication class and preferred term. Usage of Aspirin / antiplatelet drugs and Heparin / anticoagulant drugs up to 7 days prior to screening/stroke onset will be summarized.

Concomitant medications refer to those ongoing during the study. Concomitant medications will be summarized by medication class and preferred term. Usage of reperfusion therapy will be summarized. Reperfusion therapy includes IV or IA alteplase and/or endovascular therapy, and will be adjudicated in a medical review.

4.7 HANDLING OF DROPOUTS, MISSING/INCOMPLETE DATA, OR OUTLIERS

For the analyses of the mRS based endpoints, last observation carried forward will be used to impute missing or out of window assessments of mRS at Day 90. The mRS result carried forward needs to be on or after Day 4 to qualify for this imputation. If there is no in-window or LOCF assessment of mRS, then a late Day 90 mRS will be used if available.

ITT patients without any observed mRS past day 4 will have their Day 90 mRS simulated by a hot deck method. This will be an adjustment cells imputation (24), with the cells defined by treatment group, age (< 65 vs. ≥ 65), pre-treatment NIHSS score (0 – 2 vs. 3 – 5), and last known well time to treatment (0 – 2 hours vs. > 2 hours). For each patient with a missing mRS score, a “donor” patient will be drawn at random from the pool of patients with available mRS and who belong to the same cell as the recipient (i.e. randomized to the same treatment group and having the

Statistical Analysis Plan: Alteplase—Genentech USMA
30/ML29093 5/17/2017

same categories for age, last known well time to treatment and baseline NIHSS). The imputed mRS will then be the mRS value of the “donor”.

It is expected that only a small number of patients will need the hot deck imputation; therefore, the techniques recommended in (24) for a variance estimate that incorporates the additional variance from the missing information will not be implemented.

No imputation of missing patient reported outcomes, cognitive assessments, or the 10-meter walk test will be performed except as specified in the scoring rules for the assessment. Reasons for the assessment not being performed will be summarized by the number and percentage in each category by treatment group.

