4.4 EFFICACY ANALYSES

All efficacy analyses will be to estimate treatment effects and provide the associated two-sided 95% confidence intervals.

Statistical Analysis Plan: Alteplase—Genentech USMA
13/ML29093 5/17/2017

Endpoints based on mRS will generally use imputation to achieve the complete ITT set, with the exception of the repeated measures modeling. Other efficacy variables will use all available data in the ITT population.

Assessment of efficacy will be conducted based on endpoints collected during the Day 90 visit. The protocol allows this visit to be scheduled within 14 days of the target 90 days post-treatment; however, a wider window of 30 days will be adopted for the purpose of efficacy analysis.

More details of imputation approach for mRS are provided in Section 4.7 and Appendix D.

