4.4.1 Primary Efficacy Endpoint

The primary efficacy analysis will estimate the effect of treatment with IV alteplase therapy and with the standard medical care (aspirin) in AIS patients with mild symptoms. The primary efficacy outcome is derived from the mRS.

The mRS is an assessment of disability with values from 0 (no symptoms at all) to 5 (severe disability); death will be scored as a '6'. The mRS is collected at 30 and 90 days after start of study drug administration. If death occurs prior to an assessment day (Day 30 or Day 90), the mRS will be considered available and will be set to 6.

The proportion of patients within each treatment group with a favorable outcome, defined by mRS of 0 or 1 at 90 days post-randomization, will be estimated in the IV alteplase arm and in the standard medical care arm. Reasons for not performing the assessment of mRS at Day 90 will be summarized.

The difference in proportions between the two groups will be estimated using the risk difference. The risk difference will be obtained from a linear model with the binary mRS 0-1 outcome as the response, treatment, and age, time from last known well to treatment, and baseline NIHSS as continuous covariates. Quadratic terms for the continuous covariates may be added to the model, if the Wald p-value for the quadratic term is <0.1. No interactions among the covariates will be included in this model.

A common approach for implementation of this model is binary regression, a GLM with the Bernoulli distribution for the outcome and the identity link function. This

Statistical Analysis Plan: Alteplase—Genentech USMA
14/ML29093 5/17/2017

model has a possibility of non-convergence when the estimated response probability falls outside of the (0,1) interval. To circumvent the non-convergence problem, an approach of using the ordinary least squares with a robust standard error is used in this study. It was shown that if a robust standard error is used with the ordinary least squares estimation, the estimate of the risk difference is equal or similar to the estimate from the GLM with an identity link for Bernoulli outcome approach (22, 23).

The primary efficacy analysis will include all ITT patients, with patients grouped according to the treatment assigned at randomization. Missing or out of window mRS at Day 90 will be imputed with LOCF or late Day 90 mRS, if available, or simulated with a hot deck method (see Section 4.7 for handling of missing mRS).

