Appendix B
Schedule of Assessment and Study Flow Chart

ASSESSMENTS	Screening and Baseline (Visit 1)	Study Drug Administration	22–36 Hours from Start of Study Drug Administration (Visit 2)	Day 5 (or Discharge if Sooner) (Visit 3)	30 Days (±7 Days) Phone Call (Visit 4)	90 Days (± 14 Days)/ Study Completion Visit (Visit 5)	Early Discontinuation (Phone call if possible)
Informed consent	X						
Review of eligibility	X						
Medical history and baseline conditions ^a	X						
Demographics	X						
Physical examination ^b	X						
Vital signs ^c	X						
Complete blood count ^d	X						
Coagulation status ^e	X						
Pregnancy test ^f	X						
Serum blood glucose ^g	X						
Imaging modality sensitive to presence of intracranial hemorrhage (either CT or MRI with DW MRI, either SW or GRE, and FLAIR images). Visit 2 MRIs should also include T1 and T2 sequences ^h	X		X				
NIHSS score ⁱ	X		X	X		X	
Study drug administration		X					

Statistical Analysis Plan: Alteplase—Genentech USMA
39/ML29093 5/17/2017

ASSESSMENTS	Screening and Baseline (Visit 1)	Study Drug Administration	22–36 Hours from Start of Study Drug Administration (Visit 2)	Day 5 (or Discharge if Sooner) (Visit 3)	30 Days (±7 Days) Phone Call (Visit 4)	90 Days (± 14 Days)/ Study Completion Visit (Visit 5)	Early Discontinuation (Phone call if possible)
Discharge location				X			
Patient survival			X	X	X	X	X
mRS ^j					X	X	
GOS						X	
BI ^k						X	
EQ-5D ^k						X	
CES-D ^k						X	
SIS-16 ^k						X	
Cognitive assessment ^l						X	
Walking speed ^m						X	
Concomitant medications ⁿ	X		X	X	X	X	X
Assessment of pregnancy					X		
Adverse event ^o	X		X	X	X	X	X

BI = Barthel Index; BNT =Boston Naming Test; CES-D = Centers for Epidemiologic Studies, Depression; CT =computed tomography; DW MRI= diffusion-weighted MRI; European Quality of Life = EQ-5D; FLAIR = fluid-attenuated inversion recovery; GOS = Glasgow Outcome Scale; GRE= gradient echo; HVLT-R=Hopkins Verbal Learning Test-Revised; ICH = intracranial hemorrhage; INR = international normalized ratio; MRI=magnetic resonance imaging; mRS modified Rankin Scale; NIHSS= NIH Stroke Scale; Stroke Impact Scale-16= SIS-16; SWMRI= susceptibility-weighted MRI; WAIS III =Wechsler Adult Intelligence Scale III.

^a Includes smoking history and stroke history.

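### The Day 90 mRS rule carries forward any score from Day 4 on, ranks it above an observed late score, and is never tested on the risk difference

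*SAP*

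**What the plan says.** SAP Section 4.7 states that "last observation carried forward will be used to impute missing or out of window assessments of mRS at Day 90". The only condition on the carried score is its date: "The mRS result carried forward needs to be on or after Day 4 to qualify for this imputation". The next step in the order is: "If there is no in-window or LOCF assessment of mRS, then a late Day 90 mRS will be used if available". Patients with no mRS after Day 4 go to a single hot-deck draw within cells of arm, age, NIHSS and time to treatment.

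Section 4.4.1 applies this to the primary analysis ("Missing or out of window mRS at Day 90 will be imputed with LOCF or late Day 90 mRS, if available"), and Table 2 lists it for mRS 0-1, ordinal mRS, mRS 0 and the mRS component of the global outcome. Deaths are outside the rule, because for a patient who has died "the mRS will be considered available and will be set to 6".

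On timing, Section 4.4.1 says "The mRS is collected at 30 and 90 days after start of study drug administration". The schedule in Appendix B agrees. It lists mRS at the Day 30 call (±7 days) and at the Day 90 visit, and at neither the Day 5 visit nor early discontinuation. For Day 90, Section 4.4 says that "a wider window of 30 days will be adopted for the purpose of efficacy analysis".

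**The concern.** Three features of the rule lack support in the plan.

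- **The floor.** No mRS is scheduled between Day 4 and Day 22. The floor can therefore only admit unscheduled scores from the acute phase, and the SAP gives no reason for it.
- **The assumption of no change.** Carrying a Day 30 score forward assumes that the patient does not cross the 0-1 boundary before Day 90. The plan's own repeated-measures model (Section 4.4.3.1, Appendix D) gives Day 30 and Day 90 separate intercepts, so it allows the favorable rate to differ between them. Most patients should have both scores, so the trial can estimate the transition from its own data.
- **The order.** Under Section 4.7 a Day 30 score displaces an observed Day 90 score that came in after the window closed.

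Superiority testing has been set aside, so the trial delivers an estimate and its confidence interval. A carried value enters both as if it had been observed. If patients still change after Day 30, the favorable proportions are misstated. The risk difference is biased if the arms differ in the number of such patients or in how they change.

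**Working it through.** **1. Reproduce the plan's figure that uses the missing rate (Table 1).** Inputs: 290 effective patients (145 per arm), control rate 74% in confirmed strokes, 10% mimics with 80% favorable, 1% concomitant tPA, one-sided 0.025.
- Control rate: 0.9 × 0.74 + 0.1 × 0.80 = 0.746.
- Alteplase rate: 0.746 + 0.9 × effect × 0.99.
- Two-proportion power at effects of 7, 8 and 9 points: 24.6%, 31.1% and 38.4%. The plan states 25%, 31% and 38%.

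Table 1 reproduces, so its inputs can be used below.

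**2. Patients without a Day 90 outcome.** 0.074 × 313 = 23.2, about 23 (313 − 290 = 23). The SAP does not say how many of these have an earlier mRS, a late mRS or neither.

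**3. Length of the carry-forward.**
- At the rule's limit: 90 − 4 = 86 days.
- From the scheduled call: 90 − 23 = 67 to 90 − 37 = 53 days.
- If the wider window is read as ±30 days, scores from Days 60 to 120 count as in window. A late score is then one after Day 120.

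**4. Size of the effect.** Let m be the number of patients with only an early score and r the net change in mRS 0-1 between that score and Day 90. Neither is in the SAP. I assume m = 6 to 18 and r = 5 to 15 points, with 313 / 2 = 156.5 patients per arm.
- Overall favorable rate, m × r / 313: 6 × 0.05 / 313 = 0.10 points; 18 × 0.15 / 313 = 0.86 points.
- Risk difference with a 2:1 split of these patients by arm, (m/3) × r / 156.5: 2 × 0.05 / 156.5 = 0.06 points; 4 × 0.10 / 156.5 = 0.26 points (m = 12, r = 10); 6 × 0.15 / 156.5 = 0.58 points.
- One patient on the wrong side of 0-1: 1 / 156.5 = 0.64 points.

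**5. Yardstick.** Standard error of the unadjusted risk difference at N = 313:
- Rates 0.746 and 0.746 + 0.9 × 0.09 = 0.827: √[(0.746 × 0.254 + 0.827 × 0.173) / 156.5] = 4.6 points, a 95% half-width of 9.0.
- No difference, both 0.746: √[2 × 0.746 × 0.254 / 156.5] = 4.9 points.

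The assumed shifts are about 1% to 13% of one standard error.

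**6. Does any planned analysis test the rule?** By Section 4.4.3.1, the unadjusted, propensity-adjusted and logistic analyses reuse the same imputed values. The only mRS 0-1 analysis without imputation is the exploratory GEE model. It reports an odds ratio, with one treatment effect shared by Day 30 and Day 90, so it cannot check the Day 90 risk difference.

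**7. Are there enough donors?** Assume about 25% of patients have mRS 2 or more at Day 30. Matching on arm and Day 30 class leaves about 145 × 0.25 = 36 donors per arm in the smaller class. Crossing with the eight age/NIHSS/time cells leaves 145 / 8 × 0.25, about 4 to 5 on average.

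**The case against.** The case for leaving the rule alone is mainly about size. The top of the range needs 18 of about 23 patients to have only an early score, a 15-point net transition and a 2:1 split, all together. No test or decision threshold depends on the result. The wide efficacy window already rescues scores from Days 60 to 120. The GEE model uses Day 30 scores without treating them as Day 90 values. All of this stands. It limits the weight of the point but does not justify the Day 4 floor, the precedence over an observed late score, or the absence of any risk-difference check.

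Replacing carry-forward with one donor draw would also still treat an imputed value as observed, would add random noise, and could run short of donors in fine cells. That stands too, and the fix has to deal with it.

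A reader might infer three stronger things that the document does not support:
- **That values are typically frozen for 86 days.** That needs an unscheduled mRS on Day 4. From the scheduled call the span is 53 to 67 days.
- **That the bias in the risk difference has a known direction.** A net transition would move the overall favorable rate one way. The sign for the risk difference depends on the unknown split by arm, and it cancels if numbers and transitions are equal.
- **That the risk difference could move by up to 7.4 points.** That would need every missing patient in one arm to be carried forward and misclassified the same way. The 7.4% is not broken down by imputation route.

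**Conclusion.** The point holds as a weakness in how the primary endpoint is constructed. The Day 4 floor matches no scheduled mRS, a carried score outranks an observed late one, and the assumption of no change is neither justified nor tested on the risk difference. The likely shift is about 0.1 to 0.6 points against a standard error of 4.6 to 4.9. It rests on assumed values for the number of early-only patients, their net transition and the split by arm, and its direction is unknown. On these figures it would not change the trial's conclusion by itself. It should still be corrected, because the estimate and its interval are the trial's main product and the change is cheap.

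**What to change.** Rewrite the order in Section 4.7, and align Section 4.4.1 and Table 2 with it:

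1. Use an in-window Day 90 mRS, with deaths set to 6 as now.
2. Otherwise use an observed late Day 90 mRS, ahead of any carried or donated value.
3. Otherwise, for a patient with a Day 30-window mRS, draw the Day 90 mRS from donors in the same randomized arm and the same Day 30 class (0-1 or 2 and above) who have an observed in-window Day 90 mRS. Match on arm and Day 30 class only, or state a rule for collapsing the age/NIHSS/time cells.
4. Otherwise, including when the only score is from before Day 23, use the existing baseline-cell hot deck. Never use such a score as a Day 90 value.

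The text should also say where a score that falls between the two windows (Days 38 to 59) belongs.

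Repeat the draws as multiple imputation, so that the confidence interval reflects imputation uncertainty. Report carry-forward as a labelled sensitivity analysis of the risk difference.

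The cost is SAP wording, slightly more programming and a few more simulated values. Section 1 says the SAP is to be final before database lock and unblinding, so the change can be made without sight of results by arm.
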